#### **3.2. Number of Subjects**

A total of approximately 95 subjects will be enrolled at approximately 25 US sites.

#### **3.3. Treatment Assignment**

Subjects will be randomized 1:1:1:1 to ATI-501 Oral Suspension 400 mg, 600 mg, 800 mg or Placebo Oral Suspension twice-daily for 24 weeks followed by a 4-week post-treatment follow up period.

#### **3.4. Dose Adjustment Criteria**

Subjects should not modify the study medication dosage or frequency without the investigator's prior approval. All study medication modifications must be reported on the appropriate eCRF. If study medication intolerance or safety issue occurs, after consulting with the Aclaris Therapeutics, Inc. Medical Monitor (see page 1), the investigator or designee may direct the subject to modify the study medication frequency from twice-daily to once-a-day. If the subject cannot take the study medication twice-daily for more than 4 consecutive days, other dose modifications and continuation in the study must be reviewed with the Medical Monitor.

### 3.4.1. Safety Criteria for Adjustment or Stopping Doses

#### 3.4.1.1. Study Medication Interruption

Treatment with ATI-501 Oral Suspension should be temporarily interrupted in the event of severe adverse events considered related to ATI-501, or in the event of one or more of the abnormal laboratory values listed in [Table 2](#).

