**Table 2: Study Medication Interruption Criteria**

Laboratory Test	Hold Study Medication if:	Resume Study Medication if:
WBC count	< 2 x 10  /μL	≥ 2.5 x 10  /μL
ANC	< 1 x 10  /μL	≥ 1.5 x 10  /μL
Lymphocyte count	< 0.5 x 10  /μL	≥ 0.75 x 10  /μL
Platelet count	< 75 x 10  /μL	Returns to Baseline values
Hemoglobin	< 8 g/dL or a decrease > 2g/dL	≥ 10 g/dL
AST or ALT	> 3 x ULN	< 2 x ULN or within 20% of Baseline values
Serum creatinine	>2 x ULN	<1.5 x ULN or within 10% of Baseline value

Subjects with one or more of the Screening (Visit 1) laboratory values meeting the Study Medication Interruption Criteria found in [Table 2](#) must have repeat lab testing performed with results meeting the minimum criteria for resumption in order to initiate treatment at Baseline (Visit 2).

During treatment, if a subject has one or more of the abnormal laboratory values noted in [Table 2](#), the investigator or designee upon receipt and review of the central laboratory report should instruct the subject to hold study medication dosing. The investigator or designee should ask the subject about symptoms, concomitant illnesses and medications and repeat the test(s) as soon as possible. The Medical Monitor must be notified of dose interruptions due to SAEs considered related to study medication or laboratory abnormalities noted in [Table 2](#).

If the retest confirms the abnormal laboratory value, then the study medication should continue to be held followed by repeat testing once a week or sooner at the discretion of the investigator. The subject should be followed until the laboratory abnormality(s) returns to normal or to Baseline values.

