#### 3.4.1.2. Study Medication Discontinuation

Study medication should be permanently discontinued in the event of any of the following:

- Subject's study medication blinding is broken
- Severe infection requiring parenteral antimicrobial therapy or hospitalization
- Symptomatic herpes zoster

- Malignancy
- Anaphylactic or severe allergic reaction
- WBC Count:  $< 1 \times 10^3/\mu\text{L}$  or second occurrence of  $< 2 \times 10^3/\mu\text{L}$
- ANC:  $< 0.5 \times 10^3/\mu\text{L}$  or second occurrence of  $< 1 \times 10^3/\mu\text{L}$
- Lymphocyte count:  $< 0.3 \times 10^3/\text{L}$  or second occurrence of  $< 0.5 \times 10^3/\mu\text{L}$
- Platelet count:  $< 50 \times 10^3/\mu\text{L}$  or second event of  $< 75 \times 10^3/\mu\text{L}$  – in each case, value should be confirmed by retesting before treatment discontinuation
- Hemoglobin:  $< 6.5 \text{ g/dL}$  or second occurrence of  $< 8 \text{ g/dL}$  – in each case, value should be confirmed by retesting before treatment discontinuation
- AST or ALT:
  - $> 5 \times \text{ULN}$  persisting for 2-weeks of study medication interruption or second event of  $> 5 \times \text{ULN}$
  - $> 3 \times \text{ULN}$  with total bilirubin  $> 2 \times \text{ULN}$  or symptoms of hepatocellular injury [fatigue, nausea, vomiting, right upper quadrant pain or tenderness, fever, rash and/ or eosinophilia ( $> 5\%$ )].
- Serum creatinine:  $> 2 \times \text{ULN}$  persisting for  $> 2$  weeks of treatment discontinuation or second occurrence of  $> 2 \times \text{ULN}$

The continued treatment of subjects who experience other serious or severe adverse events considered related to study treatment should be discussed with the Sponsor's medical monitor.

Any subject who develops any of the following ECG findings during the active treatment phase will be instructed to stop study medication and will be withdrawn from the study:

- A post-study medication ECG result where the evaluator's interpretation shows any of the following:
  - Clinically significant rhythm disturbance other than sinus rhythm or ectopic supraventricular rhythm (ectopic atrial rhythm)
  - Clinically significant conduction disturbance including PR  $> 240\text{msec}$ , pre-excitation (delta wave and PR  $< 120\text{msec}$ ), second degree or higher AV block

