#### **8.2.1.2. Serious Adverse Event (SAE)**

A serious adverse event is an AE occurring during any study phase (i.e., Baseline, Treatment, Washout, or Follow-up), and at any dose of the investigational product, comparator or placebo, that fulfills one or more of the following:

- Results in death
- It is immediately life-threatening
- It requires in-patient hospitalization or prolongation of existing hospitalization

- It results in persistent or significant disability or incapacity
- Results in a congenital abnormality or birth defect
- It is an important medical event that may jeopardize the patient or may require medical intervention to prevent one of the outcomes listed above.

The term “life threatening” refers to an event in which the subject was at risk of death at the time of event; it does not refer to an event that hypothetically might have caused death if it were more severe.

Important medical events are those that may not be immediately life threatening, result in death or hospitalization, but are clearly of major clinical significance and may jeopardize the subject or require intervention to prevent one of the outcomes listed in the SAE definition above. These should also usually be considered serious.

All SAEs that occur from the time of informed consent until 30 days following the cessation of study medication dosing, whether or not they are related to the study, must be recorded on the SAE forms provided by Aclaris Therapeutics, Inc.

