#### **8.3.2. Severity**

The investigator is to define the severity of each AE using the following definitions as a guideline. The investigator will consider the range of the possible severity of the event and identify the severity that is the most appropriate according to her/his medical judgment.

**Mild** – Awareness of signs or symptom, but easily tolerated

**Moderate** – Discomfort, enough to cause interference with usual activity

**Severe** – Incapacitating with inability to perform usual activity

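### The rules for interrupting study medication, notifying the Medical Monitor and reviewing continued treatment use three different terms (severe; SAE; serious or severe) and need to be reconciled

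*Protocol*

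**What the plan says.** Three protocol sentences govern study medication after a related adverse event.

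- **Interruption.** Section 3.4.1.1 says treatment should be "temporarily interrupted in the event of severe adverse events considered related to ATI-501", or when a laboratory value in Table 2 is reached.
- **Notification.** Below Table 2, in the same section: "The Medical Monitor must be notified of dose interruptions due to SAEs considered related to study medication or laboratory abnormalities" listed in that table.
- **Continued treatment.** Section 3.4.1.2, after the list of permanent-discontinuation events, names the medical monitor at the sponsor as the person to consult: "The continued treatment of subjects who experience other serious or severe adverse events considered related to study treatment should be discussed".

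The two terms are defined separately. Section 8.3.2 makes severe the top grade of intensity: "Incapacitating with inability to perform usual activity". Section 8.2.1.2 makes serious depend on outcome, with a list that includes death, immediate threat to life, important medical events and this item: "It requires in-patient hospitalization or prolongation of existing hospitalization". No intensity grade is needed for an event to be serious. The abbreviation list expands SAE as serious adverse event, so SAE cannot be read as shorthand for severe.

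**The concern.** A site that follows Section 3.4.1.1 from top to bottom meets one trigger for interrupting the drug and another for telling the Medical Monitor that it was interrupted. Because severe and serious are not interchangeable under the protocol's own definitions, an event can meet one trigger and not the other. A related event that puts a subject in hospital but is graded moderate is serious and not severe. A related event that incapacitates a subject for a day at home may be severe and not serious.

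What is at stake is consistent handling of related events. Safety and tolerability are part of the primary objective (Section 2.1), dosing is blinded for 24 weeks, and about 25 sites apply the rules (Section 3.2). Earlier multiple dosing lasted 14 days in healthy volunteers (Section 1.3), so sites have little prior experience to settle an unclear rule.

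**Working it through.** No figure in the plan depends on this point, so the check is a comparison of the text.

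**Step 1: set aside events that other rules already decide.** Table 2 laboratory values trigger a hold whatever the adverse-event grade. Section 3.4.1.2 requires permanent discontinuation for named events. Some of these, such as malignancy and symptomatic herpes zoster, carry no grade. Others carry their own qualifier, such as "Severe infection requiring parenteral antimicrobial therapy or hospitalization". The same section lists ECG findings that end treatment and participation. The rest of the check concerns related events outside these three lists.

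**Step 2: cross-classify what remains.**

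| Related event | Interruption (3.4.1.1) | Mandatory notice of the interruption (below Table 2) | Discussion of continued treatment (3.4.1.2) |
|---|---|---|---|
| Serious and severe | Instructed | Covered | Covered |
| Serious, not severe | Not instructed | Covered if an interruption is made | Covered |
| Severe, not serious | Instructed | Not covered | Covered |
| Neither | Not instructed | Not covered | Not covered |

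The first and last rows are consistent across the interruption and notification sentences. The second and third are not: 2 of 4 combinations. In the second row, the notification sentence speaks of interruptions due to SAEs, but no sentence tells the site to make one. In the third, the site is told to interrupt, but the sentence that makes notice mandatory does not reach that interruption.

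**Step 3: look for other cover.**

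- Section 3.4.1.2 covers both mismatched rows. It is worded as should, where the notification sentence says must. It sets no time for the discussion and does not say whether dosing goes on until it takes place.
- Section 3.4 allows a reduced dosing frequency for a safety issue after consulting the Medical Monitor. It requires Medical Monitor review if twice-daily dosing is not possible for more than 4 days in a row. Read naturally, this brings longer holds in the third row to the monitor; holds of 4 days or less are not reached by that requirement.
- Section 8.3.5 applies to every SAE, related or not and whatever its grade. The investigator must act medically to protect the subject, inform the Safety Monitor at once and send the forms within 24 hours. This covers the second row for reporting. It gives no express instruction on study medication.
- Section 4.3 lets the investigator remove a subject from the study when staying is not in that subject's interest.

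**Step 4: can the size be estimated?** No. Section 1.3 reports no SAEs among 186 healthy volunteers in eight Phase 1 studies, with multiple dosing limited to 14 days. That gives no rate of related serious or severe events for patients over 24 weeks, and nothing on how often the two classifications disagree.

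**The case against.** The strongest reply is that this is a wording mismatch with little consequence. The notification sentence is conditional: it concerns interruptions that are due to SAEs and does not say that every SAE causes one. It can be met by events that are both serious and severe, or by a hold the investigator chooses to make. Around it stand the discussion rule in Section 3.4.1.2, the review rule in Section 3.4 and the SAE duties in Section 8.3.5. Much of this stands, and it limits the point.

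It rules out three stronger inferences that a reader might draw:

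- *A related serious event not graded severe has no rule at all, so the subject simply stays on drug.* The documents do not support this. Some such events lead to permanent discontinuation or to a laboratory or ECG rule, and for the rest Sections 3.4.1.2 and 8.3.5 require attention. What is missing is an express interruption instruction.
- *A hold for a severe, non-serious event never reaches the monitor.* Section 3.4.1.2 calls for discussion, and Section 3.4 makes review mandatory beyond 4 days. What is missing is cover by the mandatory notification sentence, which matters most for short holds.
- *Holds will differ between sites and distort the comparison of dose arms.* Nothing in the documents shows this. That they could differ is as far as the text goes.

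What the reply does not remove is the mismatch itself. Section 3.4.1.2 names both terms together, which shows that the protocol treats them as distinct, and none of the surrounding rules states the dosing status until the discussion.

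**Conclusion.** The point holds as an internal inconsistency in the safety rules. Interruption, mandatory notification and continued-treatment review rest on different terms, and 2 of the 4 combinations of seriousness and severity receive actions that do not match. This applies only to related events outside Table 2, the permanent-discontinuation list and the ECG stopping list, and other sections give partial cover. The count of 2 in 4 describes the rules; it says nothing about how many subjects are affected.

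The conclusion assumes that the terms carry their defined meanings in Sections 8.2.1.2 and 8.3.2, and that the review rule in Section 3.4 applies to a hold made under Section 3.4.1.1. If it does not, the cover for severe, non-serious events is thinner. The correction is worth making because it aligns stated safety rules at low cost, not because harm or bias has been shown.

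**What to change.** The sponsor should reconcile the interruption sentence in Section 3.4.1.1, the notification sentence below Table 2 and the continued-treatment sentence in Section 3.4.1.2, so that all three use the same defined term or terms. The sentences should also be consistent on the subject's dosing status until the discussion with the Medical Monitor. Which events trigger a hold, and how dosing resumes after one, are the sponsor's medical decisions, and this review takes no position on them.

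The cost is wording in Sections 3.4.1.1 and 3.4.1.2, with the ethics approval that Section 12.1 requires before an amendment is used. The downside is possibly a few more notifications to the Medical Monitor. No analysis or sample size changes.

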**Table 2: Study Medication Interruption Criteria**

Laboratory Test	Hold Study Medication if:	Resume Study Medication if:
WBC count	< 2 x 10  /μL	≥ 2.5 x 10  /μL
ANC	< 1 x 10  /μL	≥ 1.5 x 10  /μL
Lymphocyte count	< 0.5 x 10  /μL	≥ 0.75 x 10  /μL
Platelet count	< 75 x 10  /μL	Returns to Baseline values
Hemoglobin	< 8 g/dL or a decrease > 2g/dL	≥ 10 g/dL
AST or ALT	> 3 x ULN	< 2 x ULN or within 20% of Baseline values
Serum creatinine	>2 x ULN	<1.5 x ULN or within 10% of Baseline value

Subjects with one or more of the Screening (Visit 1) laboratory values meeting the Study Medication Interruption Criteria found in [Table 2](#) must have repeat lab testing performed with results meeting the minimum criteria for resumption in order to initiate treatment at Baseline (Visit 2).

During treatment, if a subject has one or more of the abnormal laboratory values noted in [Table 2](#), the investigator or designee upon receipt and review of the central laboratory report should instruct the subject to hold study medication dosing. The investigator or designee should ask the subject about symptoms, concomitant illnesses and medications and repeat the test(s) as soon as possible. The Medical Monitor must be notified of dose interruptions due to SAEs considered related to study medication or laboratory abnormalities noted in [Table 2](#).

If the retest confirms the abnormal laboratory value, then the study medication should continue to be held followed by repeat testing once a week or sooner at the discretion of the investigator. The subject should be followed until the laboratory abnormality(s) returns to normal or to Baseline values.

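### In Protocol Table 2 a single haemoglobin result can meet both the hold cell and the resume cell, and no precedence or reference value is stated

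*Protocol*

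**What the plan says.** Protocol 3.4.1.1 requires a temporary interruption "in the event of one or more of the abnormal laboratory values listed in" Table 2, so one qualifying result is enough. In the haemoglobin row the hold cell reads "< 8 g/dL or a decrease > 2g/dL". The resume cell is a single absolute floor of 10 g/dL, with no condition on the size of the fall. The row does not say what the decrease is measured from. The platelet, AST/ALT and creatinine rows do refer to Baseline, in their resume cells.

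The text under the table sets the sequence. On a qualifying result the investigator "should instruct the subject to hold study medication dosing", asks about symptoms, illnesses and medication, and repeats the test. The Medical Monitor must be told of interruptions caused by Table 2 abnormalities. Then: "If the retest confirms the abnormal laboratory value, then the study medication should continue to be held", with further tests weekly or sooner. The next sentence is "The subject should be followed until the laboratory abnormality(s) returns to normal or to Baseline values". It governs follow-up and is not written as a condition for restarting.

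Section 3.4.1.2 makes a second haemoglobin below 8 g/dL a reason for permanent discontinuation. It does not mention a repeated fall of more than 2 g/dL.

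**The concern.** A hold rule and a resume rule should not both be true of the same result. Here the hold rule can be met through a fall from the subject's own starting point, while the resume rule looks only at the current level. A subject who starts well above 12 g/dL can lose more than 2 g/dL and still be at or above 10.

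The consequence is uncertainty about when to restart. One site may restart on the retest because the resume cell is met. Another may keep holding because the retest confirmed the fall. With about 25 sites, subjects with the same blood result could be managed differently. The difference would carry into recorded dose interruptions and compliance (SAP 4.3.6). It could also reach the criterion of at least 75% of study medication for the per-protocol population (Protocol 9.2, SAP 5.3), which supports the sensitivity analysis of the primary endpoint.

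**Working it through.** The plan gives no figure to reproduce; this is a logical check of one table row.

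**Inputs.** Let B be the reference haemoglobin and V the current result, both in g/dL.
- Hold (Table 2): V < 8, or B − V > 2.
- Resume (Table 2): V ≥ 10.
- Entry limits: Exclusion 14 sets numeric floors for neutrophils and platelets only, so nothing excludes B above 12.

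**Where both are true.** V < 8 and V ≥ 10 cannot both hold, so the absolute limb never overlaps. The relative limb gives V < B − 2. Combined with V ≥ 10, the overlap is 10 ≤ V < B − 2. It is non-empty exactly when B − 2 > 10, that is, when B > 12.

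**Results, in steps of 0.1 g/dL** (the reference values are illustrative, because the documents give no haemoglobin distribution):

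| Reference B | Results meeting both cells |
|---|---|
| 12.0 or below | none |
| 12.5 | 10.0 to 10.4 |
| 13.0 | 10.0 to 10.9 |
| 14.0 | 10.0 to 11.9 |
| 15.0 | 10.0 to 12.9 |
| 16.0 | 10.0 to 13.9 |

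**One subject followed through.** Take B = 14.0 and a result of 11.5. The fall is 14.0 − 11.5 = 2.5, so dosing is held and the test repeated. The retest is again 11.5. Measured from the same reference, it confirms the fall, so the text says to go on holding. It is also at least 10, so the resume cell is met. If the site restarts and the next scheduled blood count (Table 3 has one at every visit) is still 11.5, the hold is triggered again.

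**The unstated reference.** Take a Baseline of 14.0, a previous visit of 12.5 and a current result of 11.5. Measured from Baseline the fall is 2.5, which is a hold. Measured from the previous visit it is 12.5 − 11.5 = 1.0, which is not.

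**Possible effect on compliance.** SAP 4.3.6 computes compliance as exposure days minus days with fewer doses than expected, divided by exposure days. Assume dosing spans 24 × 7 = 168 days, held days count as short days, and dosing is otherwise complete. A 7-day hold gives (168 − 7)/168 = 95.8%. A 56-day hold gives (168 − 56)/168 = 66.7%. The 75% line is crossed once the hold exceeds 0.25 × 168 = 42 days. Neither document says that the per-protocol criterion uses this formula, so this shows only what is possible.

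**The case against.** The best defence is that the columns are sequential: the first triggers a hold, and the second applies only later. The sentence on confirmed retests then acts as a tie-break, because a retest at 11.5 against 14.0 still shows the fall. That is a reasonable reading, but the protocol does not state it. The retest is the point at which the resume cell would be consulted, and nothing ranks the cell against the sentence. The follow-up sentence does not settle it either, since it sets no restart condition.

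Other parts of the defence stand, and they rule out several stronger inferences:
- **That the decrease limb is idle at or above 10 g/dL.** It is not. It still triggers the hold, the enquiry, the retest and notification.
- **That study drug exposure would differ.** SAP 4.3.6 defines exposure as last dose date minus first dose date plus 1, so a temporary hold followed by a restart leaves it unchanged. SAP 6.1 also names no dose-interruption table, although the term is defined.
- **That central oversight has a gap.** Haemoglobin holds must be reported to the Medical Monitor. There is a wording mismatch nearby: interruption applies "in the event of severe adverse events considered related to ATI-501", while notification covers "dose interruptions due to SAEs considered related to study medication", and severe and serious are different attributes. However, 3.4.1.2 sends continued treatment after other related events of either kind to the Medical Monitor for discussion.
- **That a low starting value, such as 9.5 g/dL, shows the same fault.** Having to reach 10 to restart is a strict limit and not an overlap.
- **That use of Table 2 at Screening is contradictory.** The decrease limb has no defined earlier value there, but no opposing instruction results.

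**Conclusion.** The point holds for the haemoglobin row. Its two cells overlap for every reference above 12 g/dL, across a band from 10 to just under the reference minus 2. On a retest in that band the protocol both continues the hold and meets its own restart condition. The retest conflict assumes that the reference stays fixed between test and retest. If the comparator moved to the latest result, a repeat at the same level would show no fall, which is another reason to name it.

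The issue is limited to the timing of restart. The number of subjects affected cannot be estimated from the documents. No sample size, power or alpha figure depends on it. It still merits correction, because it is a safety instruction that sites could follow in opposite ways and it is cheap to repair.

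**What to change.** Reconcile three pieces of text in Protocol 3.4.1.1: the haemoglobin hold cell, the haemoglobin resume cell, and the sentence on confirmed retests. After the change, no result should satisfy both hold and resume. Name the value from which the decrease is measured. The clinical team must set the limits and decide how the pieces fit together; none is proposed here.

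As a minor wording point in the same edit, align the severe-event wording of the interruption sentence with the SAE wording of the notification sentence, consistently with 3.4.1.2.

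The cost is a clarification letter or minor amendment, with no new procedures or data collection.
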